### 9.4 Association analysis of trans-impedance and intra-cochlear voltage measurements with the NRT thresholds and intra-cochlear electrode array position over time

The intra-cochlear electrode position properties will be correlated against the trans-impedance and voltage measurements as well as the NRT thresholds using pairwise Pearson product-moment correlation coefficient.

For each implanted ear the trans-impedance and voltage measurements as well as the NRT thresholds will be compared across the three measurement times (intra-operative, first activation and 3 months) to determine the stability. Any changes in one of the measurements will be compared with the others to check for co-variance.

## 10 Data Management

Data collection is performed through [REDACTED] a web-based system for electronic data capturing. Site personnel will be trained to use this system. Data validity has to be confirmed by the investigator through an electronic signature. An audit trail is kept by this system and data clarifications may be generated by the system and sponsor personnel after review of data.

[REDACTED] is a system that has been verified and validated by the vendor. Installation of the system within Cochlear has been validated as well. Study-specific implementations are validated by data management and consist of verification that all required items are included, validity of edit checks and appropriate functionality of conditional fields. The study-specific data in [REDACTED] can only be accessed by those that have been allocated their individual account, which are personnel of the investigational sites, clinical project managers, study monitors and data management.

The patient's identity and all clinical information collected during the investigation will be de-identified (coded) and kept strictly confidential in accordance with Australian and EU data protection laws. Each participant will be given a unique code and the list of codes will be kept by the investigator as described in the data privacy section.

## 11 Amendments to the CIP

No changes in the study procedures shall be effected without mutual agreement of the investigator or investigators and the sponsor. All changes must be documented by signed CIP amendment. Ethics Committee (EC) needs to approve substantial changes to the CIP.

## 12 Deviations from the CIP

The investigator is not allowed to deviate from the CIP except under emergency circumstances to protect the rights, safety and well-being of the subjects. Such deviation shall be documented and reported to the sponsor and the EC as soon as possible.

## 13 Device accountability

Not applicable. The devices used within the study are CE marked / TGA approved and part of the clinical routine (CSEP (5), the Nucleus Programming Pod, CP900 series sound processor, CI532 and CI512)

## 14 Statements of compliance

### 14.1 Declaration of Helsinki and compliance with standards

The clinical investigation shall be conducted in accordance with the ethical principles that have their origin in the Declaration of Helsinki (2013), the EN ISO 14155:2011 and any regional or national regulations, as appropriate.

### 14.2 Ethics Committee Approval

The clinical investigation shall not commence prior to the written favourable opinion or approval from the EC is obtained. Since all study hardware and software has a CE-mark and the study would not entail additional invasive or otherwise stressful examinations, no CA approval will be sought.

The investigator shall submit the final version of the Clinical investigation plan, the informed consent and all subsequently required documents to the Ethics Committee. A copy of the Ethics Committee opinion or approval shall be provided to the sponsor.

Sponsor and investigator shall continue the communication with the EC as required by national regulations, the clinical investigational plan or the responsible EC.

Any additional requirements imposed by the EC shall be followed.

The investigator shall submit the appropriate documentation if any extension or renewal of the EC approval is required. In particular substantial amendments to the clinical investigation plan, the informed consent, or other written information provided to subjects must be approved in writing by the EC.

The investigator will report to the EC any new information that may affect the safety of the subjects or the conduct of the clinical investigation. The investigator shall send written status summaries of the investigation to the EC regularly as per local EC requirements.

Upon completion of the clinical investigation, the investigator shall provide the EC with a brief report of the outcome of the clinical investigation as per local EC requirement.

The clinical investigation is covered by a clinical trial insurance meeting the requirements of the participating countries. National requirements are specified in the national Informed Consent (IC).

### 14.3 Audits and Supervision

Study sites and study documentation may be subject to quality assurance audits during the course of the clinical investigation. In addition, regulatory bodies at their discretion may conduct inspections, during and after study completion.

### 14.4 Study Records

The investigational site will receive and has to maintain an Investigators File which does include without limitation at a minimum the signed Clinical Investigation Plan, the EC approval letter, completed Informed Consent Forms, (S)AE, ADE, DD reports, Investigator copies of all CRFs, correspondence with the sponsor and third parties (if applicable) related to the Study, a subject identification list, and a site delegation and signature sheet. All study records and

source documents shall be archived at the investigational centre for at least 15 years after the end of the study.

## 15 Informed consent process

### 15.1 Obtaining informed consent

The investigator must obtain written informed consent from the subject prior to any clinical investigation related examination or activity, and after explaining the rationale for and the details, aims and objectives of the study, the risks and benefits and alternative treatments, and the extent of the subject's involvement. Ample time must be provided for the subject to inquire about details of the clinical investigation and to decide whether to participate. All questions about the clinical investigation should be answered to the satisfaction of the subject or the subject's legally acceptable representative. Subjects must not be coerced or unduly influenced to participate or to continue to participate in a clinical investigation.

Each subject and the person who conducted the informed consent discussion must sign and date the informed consent form. Where required, a witness must sign and personally date the consent form.

A copy of the information leaflet and consent form must be given to the subject. All signed Informed Consent Forms must be archived in the Investigators File at the investigational site, according to the requirements of the country's health regulations, but for a minimum of 15 years after completion of the clinical investigation.

The subject or the subject's legally acceptable representative must be informed in a timely manner if new information becomes available that may be relevant to the subject's willingness to continue participation in the clinical investigation. The communication of this information must be documented.

The investigator shall forward any amendment made to the approved subject informed consent for review to the sponsor or study monitor and any other written information to be provided to the subject, prior to submission to his EC.

### 15.2 Data Privacy

Subjects will be identified on CRFs or similar documents (for example, questionnaires) by a unique subject identification code. Completed CRFs or similar documents are confidential documents and will only be available to the sponsor and their representatives, the investigator, the investigational statistician, and if requested to the Ethics Committee and national regulatory authorities.

The investigator and site staff will not include the name of any subject in any CRF or other forms, electronic files (for example, cdx/csv files), imaging items (for example, CT Scan), publication, or submission to a regulatory authority; will not otherwise disclose the identity of any subject; and, in any CRF, will refer to each subject by his or her identification code. The identification code consists of STUDY IDENTIFIER-SiteID-PATIENT NUMBER.

- SiteID consists of country code [REDACTED] and center code [REDACTED].
- PATIENT NUMBER consecutive numbering based on the point of enrolment at each site, e.g. the first patient enrolled is - 01

## **16 (Serious) Adverse Events ((S)AE), Adverse Device Effects (ADE) and device deficiencies**

### **16.1 Definitions**

#### **16.1.1 Adverse event - AE**

Any untoward medical occurrence, unintended disease or injury or any untoward clinical signs (including an abnormal laboratory finding) in subjects, users or other persons whether or not related to the medical device. This does include events related to the medical device or the comparator as well as events related to the procedures involved.

For users or other persons this is restricted to events related to the medical device.

#### **16.1.2 Adverse device effect - ADE**

Adverse event related to the use of a medical device. This includes any adverse event resulting from insufficiencies or inadequacies in the instructions for use, the deployment, the implantation, the installation, the operation, or any malfunction of the medical device. This definition includes any event resulting from use error or from intentional misuse of the medical device.

#### **16.1.3 Serious Adverse event - SAE**

A serious adverse event is any adverse event that:

- led to a death,
- led to a serious deterioration in the health of the subject that either:
  - resulted in a life-threatening illness or injury, or
  - resulted in a permanent impairment of a body structure or a body function, or
  - required in-patient hospitalization or prolongation of existing hospitalization, or
  - resulted in medical or surgical intervention to prevent life threatening illness or injury or permanent impairment to a body structure or a body function.
- led to foetal distress, foetal death or a congenital abnormality or birth defect.

Planned hospitalization for a pre-existing condition, or a procedure required by the CIP, without serious deterioration in health, is not considered a serious adverse event.

This includes device deficiencies that might have led to a SAE if a) suitable action had not been taken or b) intervention had not been made or c) if circumstances had been less fortunate. These are handled under the SAE reporting system.

#### **16.1.4 Serious Adverse Device Effect – SADE**

A serious adverse device effect is an adverse device effect that has resulted in any of the consequences characteristic of a serious adverse event.

#### **16.1.5 Device deficiency**

A device deficiency is an inadequacy of a medical device with respect to its identity, quality, durability, reliability, safety or performance. Device deficiencies include malfunctions, use errors, and inadequate labelling.

## 16.2 Reporting process for Serious Adverse Events

The investigator shall report all Serious Adverse Events without delay to the sponsor.

Name of contact person of the sponsor (Germany and Spain): [REDACTED]

Fax: [REDACTED]

Tel: [REDACTED]  
[REDACTED]

Name of contact person of the sponsor (Australia): [REDACTED]

Tel: [REDACTED]  
[REDACTED]

The sponsor has to report all SAEs and SADEs using the applicable report form as per national requirement.

The investigator has to report all SAEs and SADEs to his or her EC using the applicable report form as per national requirement.

Appropriate treatment of the subject shall be initiated but the study follow up shall continue when ethical.

## 16.3 Recording and assessment of AEs

Subjects shall be carefully monitored during the clinical investigation for potential AEs and shall be routinely questioned about adverse events at study visits.

For all adverse events sufficient information shall be obtained by the investigator and recorded in the CRF. The investigator shall attempt to assess the relationship between the device and the adverse event. Appropriate treatment of the subject shall be initiated but the study follow up shall continue when ethical.

## 16.4 Data Monitoring Committee

The decision to establish a Data Monitoring Committee (DMC) shall be guided by the risk analysis, taking into account both the risks associated with the use of the medical device and the risks associated with subject's participation in the clinical investigation. This study is a non-invasive study without any additional risks for the recipients that goes beyond the clinical routine for CI treatment with CE marked and TGA approved medical products. Therefore it is justified not to establish a DMC for the planned study.

## 16.5 List of anticipated Adverse Device Effects

For this clinical investigation the listed items in section 6.2 of this CIP are anticipated Adverse Device Effects.

Medical occurrences that are related to pre-existing conditions (for example, diabetes, cardiac problems) are considered as unexpected adverse events in the frame of the clinical investigation.

## 17 Suspension or premature termination

The sponsor may withdraw from sponsorship of the clinical investigation if,

- major non-adherence to the CIP is occurring
- it is anticipated that the subject recruitment will not be adequate to meet the objectives of the clinical investigation

Should the sponsor withdraw from sponsorship of the clinical investigation, the sponsor will continue sponsorship for the subjects already recruited into the study.

An ongoing clinical investigation can be discontinued in case of:

- device failure
- serious or intolerable adverse device effect, leading to the explant or discontinued use of the device
- subject's death
- investigator's decision
- subject's decision

## 18 Publication Policy

The clinical investigation will be registered at the public study register ClinicalTrials.gov.

Investigators will be able to publish and/or present their own data as well as processing their own data with their own algorithms throughout the study. The publishing investigator will provide the sponsor with a manuscript copy of the abstract and paper at least 30 days in advance of publication or presentation. If the publication contains information that the sponsor at his discretion finds worth protecting in the form of a patent or trademark etc., the sponsor has the right to delay the publication or presentation for 90 days.

After finishing the study it is planned to generate two joint publications by the clinical investigators and the sponsor. One journal is going to address rather the medical/surgical aspects and the other journal the technical aspects of this investigation. The responsibility for writing the publication is with the Coordinating Investigator. The authorship will be based on contribution of complete datasets and contribution to paper preparation according to the rules of the journal chosen for publication. The six Principal Investigators, the six Co-Investigators and the CPM will be part of the author list of both journals. In case the journal has a restriction of less than 11 authors, the surgeons may rather be part of the medical/surgical publication and the audiologists/engineers rather be part of the technical publication. The joint publication must be reviewed by the sponsor at least 30 days in advance to any release of publication. If the publication contains information that the sponsor at his discretion finds worth protecting in the form of a patent or trademark etc., the sponsor has the right to delay the publication or presentation for 90 days.

The Clinical Investigator Agreement will include details on publication.

All public presentations of data collected from this study shall be approved by the Clinical Project Manager prior to use. Where information is presented that was collected in a particular site, that clinical head shall also approve the use of the data. This is to avoid customers from one clinic attending a conference in another and discovering their data being presented to them without any warning.

## 20 Change History

Version Number	Date (DD Mon YYYY)	Summary of changes
1.0	10.05.2017	Approved version
2.0	14.05.2018	Extended study duration, HEARing CRC added

1.1 Overview

This is the statistical analysis plan for a multi-centre exploratory, prospective study collecting and analysing CT, NRT and trans-impedance and intra-cochlear voltage measurements.

1.2 Objectives

1.2.1 Primary objective

To explore the specificity (percentage of cases in which a true negative gives a negative result) of a candidate algorithm that has the ability to detect low incidence deviations from a normal electrode position using trans-impedance measurements.

1.2.2 Secondary objectives

1. To explore the association between the trans-impedance and intra-cochlear voltage measurements, NRT thresholds and the intra-cochlear electrode array position.
2. To investigate changes in the trans-impedance and intra-cochlear voltages along with NRT thresholds over time to identify the stability of the measurements.
3. To establish a database of trans-impedance and intra-cochlear voltages, NRT thresholds and CT images for educational, research and development purposes.

1.3 Endpoints

1.3.1 Primary endpoint

Trans-impedance and intra-cochlear voltage measurements for each electrode contact after electrode insertion with post-operative CT/DVT Scan.

1.3.2 Secondary endpoints

1. NRT thresholds for each electrode contact during surgery and pre-operative CT/DVT Scan co-registered with the post-operative CT/DVT Scan collected for the primary endpoint.
2. Trans-impedance and intra-cochlear voltage measurements and NRT thresholds for each electrode contact at first activation and 3 months post-operative
3. Validated database entry of trans-impedance and intra-cochlear voltage measurement and NRT thresholds during surgery, at first activation and three months post-operative as well as the pre-operative and post-operative CT/DVT Scans respectively.

1.4 Hypotheses

- H_0 : The specificity of an algorithm that will detect low incidence deviations from a normal intra-cochlear electrode insertion will be $< 98\%$.
- H_1 : The specificity of an algorithm that will detect low incidence deviations from a normal intra-cochlear electrode insertion will be $\geq 98\%$.

1.5 CE marked devices

The CSEP software, CP900 series sound processor and CI532 and CI512 implants are all used routinely by cochlear implant and hearing care professionals.

2 Statistics

2.1 Overview

A total of 154 patients will be assessed in the statistical analysis of the data. This will serve to collect a representative sample of the variability of surgical techniques across clinics and surgeons. The confidence interval to be used in the analyses will be a 90% two-tailed. This confidence interval was deemed to be satisfactory due to the exploratory nature of the study. The statistical analyses conducted for the primary and secondary objectives will lead to the endpoints of the study.

The statistical analysis will be conducted by [REDACTED], Cochlear).

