## 9 Statistical Considerations

### 9.1 Sample Size Calculation

An in-depth description of the statistical characterisation and correlation will be part of the Statistical Analysis Plan. Final statistical analysis will be conducted on a clean and complete database after database closure.

The candidate algorithm provides the ability to detect gross electrode position anomalies (eg. tip fold-over or electrode not in the cochlea). It provides binary outputs; a value of zero (negative result) or a value of one (positive result). A value of zero indicates that the algorithm concluded that an anomalous position has not occurred and the value of one indicates that the algorithm concluded that an anomalous position has occurred. To be useful as a tool that can replace routine use of X-rays and CT scans, the algorithm is required to have a minimal false positive rate. To ensure that this expectation is reasonably fulfilled, the 98% specificity target is set to be the lower bound of the 90% binomial confidence interval for the specificity of the algorithm. An iterative approach was adopted to estimate the required patient sample size which takes into account the likelihood of anomalous position events. It was assumed that the occurrence of a tip fold-over (the principal form of position anomaly under consideration) follows a binomial distribution with a positive probability of around 4% based on the weighted average percentage for tip fold-overs in pre-curved arrays reported by Grolman et al. 2009 and Zuniga et al. 2016. Using the Clopper-Pearson method a sample size of 154 was selected, which gives an 89% chance of 9 or less tip fold-overs taking place, resulting in at least 145 'normal' insertions. If the algorithm correctly diagnoses all 145 insertions, the lower bound of the two-tailed 90% confidence interval for specificity will be 97.97% which is approximately 98%. In other words, if the algorithm correctly identifies all 145 cases as 'normal' then it can be concluded that its specificity is 98% or better with 90% confidence.

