2.2 Sample size calculation

The goal of the candidate algorithm is to indicate to surgeons and medical staff whether an electrode tip fold-over or electrode outside cochlea appears to have occurred, which should be confirmed radiographically. A target specificity of 98% and confidence level of 90% have been selected.

The 98% specificity target initialises the calculation of the required sample size (N). Since the specificity of the algorithms can only be estimated from a sample population, there is required to be a reasonable expectation that the specificity estimate is equal to or greater than the specificity target. To ensure that the reasonable expectation is fulfilled, the 98% specificity target is set to be the lower bound of the 90% binomial confidence interval for an estimated or measured specificity of 100%. The selected sample size must fulfil this requirement. The binomial confidence interval will be calculated using the Clopper-Pearson exact method and is denoted by Equation 1 and Equation 2:

$$P_{LB} = p : \sum_{i=0}^x \binom{n}{i} p^i (1-p)^{n-i} \approx \frac{\alpha}{2}, \quad \text{for } 0 \leq p \leq P \quad (1)$$

$$P_{UB} = p : \sum_{i=x}^n \binom{n}{i} p^i (1-p)^{n-i} \approx \frac{\alpha}{2}, \quad \text{for } P \leq p \leq 1 \quad (2)$$

where P_{LB} is the lower bound of the binomial confidence interval, P_{UB} is the upper bound of the binomial confidence interval, P is the measured probability of success, p is the probability of success, n is the number of trials, i is the number of successes, x is the measured number of successes and $\alpha = 0.1$ is the level of significance for the 90% confidence interval.

In the Clopper-Pearson method, n is the unknown input in the equation. To find n requires taking into account that there may be occurrences of electrode anomalies in the sample. The range of the possible numbers of anomalies must be estimated such that there is an expected sufficient number of samples (n) to estimate specificity. The sufficient number of samples is calculated by Equation 3 and Equation 4:

$$n = N - m \quad (3)$$

$$m = i : \sum_{i=0}^N \binom{N}{i} p^i (1-p)^{N-i} \approx 0.90, \quad \text{for } 0 \leq i \leq N \quad (4)$$

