3.1 Primary objective

The primary objective of the study is to explore the specificity of an algorithm that detects low incidence anomalies such as tip fold-overs or an electrode migration. The target maximum specificity of the algorithm has been selected to be 98%. The following steps will be run to explore the specificity up to this upper bound:

1. Run the candidate algorithms on each of the patient's data
 - Patients with 'normal' insertions (89% chance of at least 145 patients)
2. Collect the output of the algorithm

- The outputs of the algorithms will be Boolean in nature; 0 represents no tip fold-over or electrode outside the cochlea and 1 represents an tip fold-over or electrode outside the cochlea
3. Count the number of patients that have been classified as not having an anomaly by the algorithm.
 4. Conduct radiographic analysis of each insertion to classify as either normal or abnormal. Document in the latter case the reason for the classification in the anomaly category. .
 5. Calculate the percentage of patients (P) that have been correctly classified as not having an anomaly
 6. Calculate the lower bound of the 90% binomial confidence interval (P_{LB}) for the true success rate (specificity) of the algorithm using Equation 1

If the calculated lower bound of the 90% binomial confidence interval around p is equal to or greater than 98%, the candidate algorithms can be stated to have an expected specificity equivalent to or greater than 98% with 90% confidence. As explained in Section 4, the candidate will have reached the upper limit of specificity of 98% with 90% confidence if 100% of at least 145 normal insertions are correctly classified as normal.

3.2 Secondary objective 1

The first secondary objective of this study is to explore the association or relationships between the trans-impedance, intra-cochlear voltage measurements and NRT thresholds and the intra-cochlear electrode position. This will be conducted by:

1. Measuring the intra-cochlear electrode array position for 22 electrodes for each patient from CT images
2. Univariate and multivariate analysis
 - a. Visualisation (descriptive statistics)
 - b. Feature extraction
 - c. Correlation and ANOVA analysis
 - d. Statistical modelling

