    # to p (lower bound) and from p to 1 (upper bound)

    # Two-tailed
    alpha_2 = alpha/float(2)

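### The primary decision uses a one-sided 95% lower bound that is reported as 90% confidence, and at 145 of 145 that bound is 97.96%, so the 98% rule is not met

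*SAP*

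**What the plan says.** **Interval.** SAP 2.1 states: "The confidence interval to be used in the analyses will be a 90% two-tailed". Its reason is given next: "This confidence interval was deemed to be satisfactory due to the exploratory nature of the study". SAP 2.2 sets alpha = 0.1, which it says "is the level of significance for the 90% confidence interval", and puts alpha/2 in each tail. The Appendix A code does the same.

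**Hypothesis and rule.** H1 (protocol 7, SAP 1.4) points one way: specificity of at least 98%. The rule in SAP 3.1 looks only at the lower limit and opens: "If the calculated lower bound of the 90% binomial confidence interval around p is equal to or greater than 98" per cent. If that holds, the algorithm may be said to reach 98% with 90% confidence.

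**Planned result.** SAP 2.2 and protocol 9.1 give a lower limit of 97.97% for 145 of 145 correct and treat it as approximately 98%. Protocol 9.1 then says of that result that "it can be concluded that its specificity is 98% or better with 90% confidence". SAP 3.1 says that with every one of at least 145 normal insertions classified correctly, "the candidate will have reached the upper limit of specificity of 98% with 90% confidence".

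**The concern.** A statement that specificity is at least 98% with 90% confidence is one-directional. A reader will normally take it as a one-sided 90% statement, with 10% in the lower tail. The calculation behind it has 5% there. The two readings give opposite answers at the planned number of normal insertions: with a 5% tail a perfect result misses 98%, and with a 10% tail it clears 98%.

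SAP 3.1 therefore contains a rule and a claim that cannot both hold for the limit as calculated. Unless this is settled before analysis, the sidedness of the primary criterion could be chosen once the number of normal insertions is known.

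**Working it through.** **Inputs.** N = 154, m = 9, n = 145 and printed limit 0.9797 (SAP 2.2); alpha = 0.10, split over two tails (SAP 2.2, Appendix A); target 98% (SAP 1.4 and 3.1); fold-over rate 0.04139 (SAP 2.2).

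**1. Reproduce the plan's figures.**
- Fold-over rate: (5 + 4)/(0.48 × 303 + 72) = 9/217.44 = 0.04139, as stated.
- Chance of 9 or fewer fold-overs in 154: 0.892, matching the stated 89%.
- When all n are correct, the Clopper-Pearson lower limit solves p^n = tail area, so the limit is (tail area)^(1/n). With a 5% tail: 0.05^(1/145) = 0.97955.
- The printed 0.9797 comes from the Appendix A search. It steps through 8,000 values of p, accepts any whose tail area is within 0.05 ± 0.002, and keeps the last. That value is 0.979747, with tail area 0.979747^145 = 0.0515.
- Equation 1 as printed sums from 0 to x, which equals 1 when x = n. The code sums from x to n, which is the correct tail for a lower limit and is the one used here.

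**2. Which one-sided level is it?** The limit at 145 of 145 under three tail areas:

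| Lower tail | One-sided confidence | Limit |
|---|---|---|
| 2.5% | 97.5% | 97.49% |
| 5% | 95% | 97.96% |
| 10% | 90% | 98.42% |

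Only the 5% tail agrees with the printed figure, apart from the search tolerance.

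**3. Error rate of requiring 145 of 145.** If true specificity is 98%, the chance of a perfect result is 0.98^145 = 0.0534. The result therefore supports 98% at 1 − 0.0534 = 94.7% one-sided confidence.

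**4. Normal insertions needed, with no false positive, for a limit of at least 98%.**
- 5% tail: ln 0.05 / ln 0.98 = 148.28, so 149. Check: 148 gives 97.996% and 149 gives 98.010%.
- 10% tail: ln 0.10 / ln 0.98 = 113.97, so 114. Check: 113 gives 97.983% and 114 gives 98.0005%.

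A perfect result on any number from 114 to 148 passes under one reading and fails under the other. A single false positive fails under both, even if all 154 insertions were normal: the limits are 96.96% (5% tail) and 97.50% (10% tail).

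**5. How likely is it that 149 normal insertions are available?** This needs 5 or fewer fold-overs among 154. At the SAP's rate that has probability 0.38, against 0.89 for at least 145. This counts fold-overs as the only exclusion and assumes no missing data. Protocol 9.3 also excludes other insertion-related events, which would lower both figures.

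**The case against.** The strongest reply is that nothing is hidden. The interval, its two-sidedness, alpha, alpha/2 and the decision rule are all written out, and protocol 9.1 names the limit as that of a two-tailed 90% interval. The 90% can be read as shorthand for that interval, in a study described as exploratory. All of this stands: the sentence in SAP 2.1 is correct in itself, and the loose wording is in protocol 9.1 and SAP 3.1.

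A reader might infer three stronger things that the documents do not support.

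- *That the test is misstated or the confidence overstated.* It is not. A bound valid at 95% is also valid at 90%, so the label understates the level. Requiring 145 of 145 has an error rate of 5.3%, slightly above 5% and well under 10%. As a one-sided 90% statement, the protocol's sentence is true at 145 of 145.
- *That the label causes the shortfall from 98%.* It does not. SAP 2.2 stops its search when the limit is approximately 98% and accepts 97.97%, while SAP 3.1 requires 98% or more. That conflict would remain if the label were perfect.
- *That the upper limit in SAP 3.1 is a slip for lower bound.* Protocol 8.1 speaks of establishing a specificity of up to 98%. Read with that, SAP 3.1 means the highest specificity the planned sample can demonstrate. The term is awkward but not an inversion.

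What the reply does not answer is SAP 3.1's claim that 145 correct out of 145 is enough. Under its own rule and its own calculation, it is not.

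**Conclusion.** The point holds in a limited form. The primary criterion is a one-sided 95% bound reported without its one-sided level. The conclusion attached to the planned perfect result does not follow from it: 97.96% exact, or 97.97% as printed, against a requirement of at least 98%. The shortfall is 0.04 percentage points, or four normal insertions (149 against 145). It matters because the rule has a hard threshold and tolerates no false positive, so this small gap decides whether the planned best case passes or fails.

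Type I error is not inflated relative to the stated 90%, and no conclusion is overstated at that level. The verdict rests on the exact Clopper-Pearson limit, on applying the threshold as written without rounding, and on 145 being the number of normal insertions analysed. With 149 or more, all correct, the rule is met as it stands.

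**What to change.** In SAP 2.2, SAP 3.1 and protocol 9.1:

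1. Keep the pre-specified limit and state that the decision uses the lower limit of a two-sided 90% interval, that is one-sided alpha 0.05 and 95% one-sided confidence.
2. Give the exact limit at 145 of 145 as 97.96%.
3. Replace the claim that 145 of 145 establishes 98% under this rule. What the result supports is specificity of at least 97.96% with one-sided 95% confidence. It also supports at least 98% at the lower one-sided 90% level, where the limit is 98.42%. State that 149 normal insertions with no false positive are needed to meet the rule as written.
4. In SAP 3.1, explain the maximum and upper limit as the highest specificity that the planned sample can demonstrate. Substituting lower bound would change the meaning.

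If the sponsor intends a one-sided 90% criterion instead, that moves the nominal one-sided error rate of the primary analysis from 5% to 10%. It should be declared and justified before analysis as a change of error rate, with SAP 2.1, the equations and Appendix A altered to match.

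Items 1 to 4 change text only and have no effect on data collection or patients. The one-sided 90% alternative changes the primary criterion.
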